STATISTICS Primary Analysis Plan	
The analysis population consists of all eligible subjects who enroll into the study. Results will be based primarily on descriptive statistics of questionnaire results. The primary endpoint is the percentage of scheduled outside-the-clinic assessments with at least one PRO fully completed out of the four questionnaires administered (the PAC-SYM, PAGI-SYM, PAC-QOL and the disease-specific questionnaire). The denominator for the percentage is the expected number of outside-the-clinic assessments (# of enrolled subjects x 3 outside-the-clinic assessments/subject). Missing PRO data will be extensively summarized including a comparison of the representativeness of the enrolled subjects against the larger CF community.
 
Constipation is defined as <3 bowel movements in the past week and/or Bristol Stool type 1 or 2. The secondary endpoint upon which the sample size is based is the number (%) of enrolled subjects with any occurrence of constipation during 1 month of follow-up. For all percentages, the 95% Confidence Interval (95% C.I.) will be calculated using the Wilson method. Summary statistics of stool frequency and type will be tabulated over time to evaluate overall disease fluctuation.
 
Individual item responses will be summarized by the number and percentage having symptoms or receiving treatment. Questionnaire scores, overall as well as by subdomain, will be based on mean scores (and 95% C.I.s) with any group comparison made via the t-test. For subjects either receiving treatment or with constipation, mean absolute change in scores from the enrollment visit will be reported including the standard deviation and 95% C.I. of the change. For select endpoints, stratification by whether the site did or did not receive DIGEST Awards (CFF grant to a gastroenterologist to focus on the comprehensive GI care of patients with CF) will be considered. Additional stratification variables include: age, CF genotype, and pancreatic status.
 
To evaluate change in PRO scores, a covariate adjusted repeated measures model of PRO scores will be fit in addition to select graphical figures showing PRO scores at scheduled assessments. No adjustment for multiplicity testing will be made. The details of all planned analyses will be outlined in the Statistical Analysis Plan (SAP).

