#### **Describe current management of GI symptoms:**

- Evaluate treatment for GI symptoms and constipation at time of enrollment visit:
  15. Number (%) of all subjects receiving treatment
  16. Number (%) of all subjects initiating treatment
  17. Number (%) of all subjects receiving treatment by Medication class/type
  18. Among subjects with GI symptoms and constipation, number (%) receiving treatment
- Evaluate symptom scores due to treatment:
  19. Mean PRO scores (also mean differences and 95% confidence interval) comparing subjects receiving treatment for GI symptoms to those not receiving treatment
  20. Among subjects receiving treatment for constipation, mean absolute change in PRO scores over time overall and by medication type/class

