### 15.4 Analysis of Secondary Endpoints

Constipation is defined as <3 bowel movements in the past week and/or Bristol Stool type 1 or 2. The secondary endpoint upon which the sample size is based is the number (%) of enrolled subjects with any occurrence of constipation during 1 month of follow-up (the period prevalence). Treatment for GI symptoms and constipation will be summarized based on the percentage of enrolled subjects receiving and initiating treatment at time of enrollment visit. To evaluate whether CF subjects are adequately treated, the number and percentage of subjects with GI symptoms and constipation on treatment will be reported. All GI related treatments will be classified by medication type/class.

Individual GI symptoms will be extracted from the PAC-SYM and PAGI-SYM questionnaires. For each GI symptom, frequency and severity will be summarized at each assessment as follows: number (%) of subjects with GI symptom, severity of GI symptom (mean score and distribution of severity score) and change in severity scores from the enrollment visit by whether subjects were receiving treatment.

Mean overall (and by sub-scale) PRO scores for PAC-SYM, PAGI-SYM and PAC-QOL at scheduled assessments will be reported including evaluation of within and between subject variability. Group comparisons of mean scores by subjects receiving/not receiving treatment and by those with/without constipation will also be made. Absolute change in PRO scores from enrollment visit to scheduled assessments will be reported based on subjects receiving/not receiving treatment for constipation. To examine these effects, figures displaying mean PRO scores by scheduled assessment will be created. Additionally, mixed effects models for repeated measures will be fit with PRO scores as the outcome and covariates for visit, treatment, pancreatic status, age group and the interaction between treatment and visit.

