Descriptive statistics will be used to summarize the total and domain scores by protocol-defined constipation. Longitudinal summaries will be provided, using mixed-effect models with participant-specific random intercepts, as well as fixed effects for weekly protocol-defined constipation status, visit, and age group. The predictor of interest is the protocol-defined constipation status. The corresponding analyses are outlined in Appendix A, Section A.5.

Evaluation of alternative CF-specific definitions of constipation:

14. Examine alternative definitions of constipation that are CF specific based on correlation with PRO questionnaires and maximizing the area under the receiver operating characteristic (ROC) curve for PAC-SYM scores
15. Number (%) reporting constipation based on patient self-assessment. Examine concordance of self-reported constipation against protocol/alternate definitions using Cohen's kappa coefficient

The corresponding analyses are outlined in Appendix A, Section A.6.

3.4.3 Current management of GI symptoms:

16. Number (%) of all participants receiving treatment at baseline
17. Number (%) of all participants initiating treatment at baseline
18. Number (%) of all participants receiving treatment by medication class/type
19. Among participants with GI symptoms and constipation, number (%) receiving treatment
20. Change in distribution of GI symptoms and stool frequency/type by GI treatment at baseline
21. Mean PRO scores (also mean differences and 95% confidence interval) by GI treatment at baseline
22. Among participants receiving or initiating treatment for constipation, mean absolute change in PRO scores over time overall and by medication type/class

The corresponding analyses are outlined in Appendix A, Section A.7.

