[2] Consider participants with both baseline and Week 2 data

[3] Consider participants with both baseline and Week 4 data

Exhibit 7.3 Changes in GI Symptoms from Baseline by Constipation Treatment

[figure not shown]
The following table shows the changes in GI symptoms from baseline at each follow-up week in subgroups defined by constipation treatment, i.e. not treated versus treated (initiating or receiving). This is a collapsed version with less details compared to the 7.3.x exhibits.

GI Symptom	Baseline Mean (95% CI)	Week 1					Week 2					Week 4				
		N [1]	Mean (95% CI)	Worsen – n (%)	No Change – n (%)	Improved – n (%)	N [1]	Mean (95% CI)	Worsen – n (%)	No Change – n (%)	Improved – n (%)	N [1]	Mean (95% CI)	Worsen – n (%)	No Change – n (%)	Improved – n (%)
Symptom 1	Not Treated	Mean (95% CI)	n	mean (CI)	n (%)	n (%)	n (%)	n	mean (CI)	n (%)	n (%)	n (%)	n	mean (CI)	n (%)	n (%)
	Treated	Mean (95% CI)	n	mean (CI)	n (%)	n (%)	n (%)	n	mean (CI)	n (%)	n (%)	n (%)	n	mean (CI)	n (%)	n (%)
Symptom 2	Not Treated															
	Treated															
...																
Symptom s	Not Treated															
	Treated															

[1] N per each follow-up week is defined as the number of participants who had data at both baseline and the follow-up week.

Exhibit 7.4 Longitudinal Summary of PAC-SYM, PAGI-SYM, and PAC-QOL Total and Domain Scores by Constipation Treatment

This table provides longitudinal summaries of the total and domain scores, for all participants and subgroups stratified protocol-defined constipation. The estimates are obtained from mixed-effect models with participant-specific random intercept, as well as fixed effects for indicator of constipation treatment, week, and age group. The predictor of interest is the indicator of constipation treatment.

A.8 Additional Exhibits for Consideration Given Data Availability and Feasibility

Exhibit: PAC-SYM, PAGI-SYM, and PAC-QOL total/domain scores by modulator use and types

Exhibits: Selected analysis on completion of ePROs, total/domain scores of PAC-SYM, PAGI-SYM, and PAC-QOL, summary of disease-specific questionnaire by 3 age groups: <12, ≥12 and <18, and ≥18 (Note: for participants <12 years old, parents or guardians would complete the ePROs)

Exhibits: Selected analysis by age groups corresponding to PROMISE for future comparison (less than 6, 6-11, 12+)

Exhibits: Repeat Exhibits 6.3-6.5 for specific symptoms of interest, e.g. nausea or bloating

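### SAP items 20–21 name GI treatment but Exhibits 7.3–7.4 group by constipation treatment only; Exhibit 7.4 drops two protocol model terms, and no described exhibit reports item 22

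*SAP*

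**What the plan says.** SAP 3.4.3 lists the outputs on current management and sends all of them to Appendix A.7.

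- Item 20: "Change in distribution of GI symptoms and stool frequency/type by GI treatment at baseline".
- Item 21: "Mean PRO scores (also mean differences and 95% confidence interval) by GI treatment at baseline". It corresponds to endpoint 19 in Protocol 5.2, "comparing subjects receiving treatment for GI symptoms to those not receiving treatment".
- Item 22, which covers only people who are on or starting a constipation drug, asks for this: "mean absolute change in PRO scores over time overall and by medication type/class".

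In A.7, Exhibit 7.1 counts GI treatment and splits it into constipation and non-constipation drugs, and Appendix D lists both kinds. Exhibits 7.3.x.y and 7.3 then show symptom change for treated versus untreated participants, where treated means constipation treatment. Exhibit 7.4 models PRO scores with a random intercept per participant and "fixed effects for indicator of constipation treatment, week, and age group".

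Protocol 15.4 gives the repeated-measures model "covariates for visit, treatment, pancreatic status, age group and the interaction between treatment and visit". Shortly before that it says: "Absolute change in PRO scores from enrollment visit to scheduled assessments will be reported based on subjects receiving/not receiving treatment for constipation". For people who are constipated or on treatment, the synopsis adds this: "mean absolute change in scores from the enrollment visit will be reported including the standard deviation and 95% C.I. of the change".

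**The concern.** Three things do not line up.

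1. Items 20 and 21 name one grouping and the exhibits use a narrower one. The group labelled untreated then contains people who are on GI treatment, and the contrast in the item is never produced.
2. Exhibit 7.4 lacks two terms of the protocol model. One of them, treatment by visit, is the term that would let the time course differ between treated and untreated participants.
3. Item 22 is listed but nothing in A.7 is described as reporting it.

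Describing current management is a secondary objective. A programmer who followed the SAP exactly would leave one listed item without an output and answer two others for a different comparison.

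**Working it through.** The plan states no figure on this point, so there is none to reproduce. The check is a comparison of text, followed by illustrations on stated assumptions.

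**Items against exhibits**

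| SAP item | Grouping asked for | Described in A.7 |
|---|---|---|
| 20, symptom change | GI treatment | 7.3.x.y and 7.3, constipation treatment only |
| 21, mean PRO scores | GI treatment | 7.4, constipation treatment only |
| 22, absolute PRO change | Constipation treatment, overall and by class | None |

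GI treatment is not shorthand for constipation treatment here. Item 22, in the same list, says constipation; Protocol endpoints 19 and 20 draw the same line; Exhibit 7.1 and Appendix D separate the two. Appendix D has 5 constipation and 12 non-constipation GI classes, and none of the 12 defines a group in 7.3 or 7.4. Yet 8 of the 12 symptoms in Appendix C (3 PAC-SYM, 8 PAGI-SYM, 1 disease-specific) are PAGI-SYM items such as nausea and reflux.

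For item 22, Exhibit 7.3 covers single symptoms, Exhibits 6.3–6.5 cover constipation status, and 7.4 has one common week effect and no class. A.8 offers PRO scores by modulator use and conditional symptom-specific repeats.

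**Model terms**

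The protocol has five: visit, treatment, pancreatic status, age group, treatment × visit. Exhibit 7.4 has three: treatment, week, age group. Without the interaction, the fitted change over time is identical in both groups by construction.

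**How many could be misgrouped (assumed shares)**

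Let p be the share on constipation treatment and q the share of the rest on other GI drugs only. The documents give neither; take p = 20%–50% and q = 20%–90% (high if enzymes count). The base is 400 enrolled, because treatment is recorded at baseline. Misgrouped = 400 × (1 − p) × q:

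- p = 50%, q = 20%: 400 × 0.5 × 0.2 = 40
- p = 20%, q = 90%: 400 × 0.8 × 0.9 = 288

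If both kinds of GI-treated participants differ from the truly untreated by D, the constipation-treatment contrast is D − qD = D(1 − q), that is 0.8D to 0.1D.

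**What the additive coefficient shows (assumed PAC-SYM paths)**

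Let treated participants start 0.5 worse and improve 0.5 more by week 4; Protocol 1.2 treats a fall of about 0.5 as minimal improvement. With complete data the coefficient is 0.5 − 0.5 × (mean share of the change reached over the modelled weeks).

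| Change occurs | Baseline modelled | Follow-up weeks only |
|---|---|---|
| All by week 1 | 0.5 − 0.5 × 0.75 = 0.125 | 0.5 − 0.5 × 1 = 0 |
| Evenly over the three follow-ups | 0.5 − 0.5 × 0.5 = 0.25 | 0.5 − 0.5 × 0.667 = 0.17 |
| All at week 4 | 0.5 − 0.5 × 0.25 = 0.375 | 0.5 − 0.5 × 0.333 = 0.33 |

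With baseline modelled, treatment × week gives −0.5 at week 4 in every row. The SAP does not say whether baseline is a modelled week. PAC-QOL is collected only at baseline and week 4, so a week effect and a random intercept for it need baseline in the model.

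**Precision of a three-group comparison**

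Half-width = 1.96 × √[(0.52 + w/4)(1/n1 + 1/n2)], with between-subject variance 0.52 (Protocol 15.7), within-subject variance w = 0.12–0.52 (assumed) and N = 352 (400 × 0.88, assuming the 12% missing rate of Protocol 15.7 applies to scores). Over the p and q ranges above, each comparison with the group on neither has a half-width of 0.16 to 0.40. The widest case is p = 50%, q = 90%, w = 0.52: 1.96 × √[0.65 × (1/158.4 + 1/17.6)] = 0.40.

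**The case against.** Protocol 15.1 and the SAP preface let the SAP modify the protocol's analyses, and SAP 2.2 puts justification of deviations in the final report. A reader might therefore say that nothing is wrong. For the two dropped terms this has force: they are an unexplained change, not a forbidden one. It does not cover items 20–22, where the SAP disagrees with itself.

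A reader might infer that Exhibit 7.4 uses the wrong treatment variable for the protocol model. The documents do not support that. In Protocol 15.4 the model follows a sentence on constipation treatment, so constipation treatment is a fair reading, and 7.4 may keep it. What is missing is the wider grouping.

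A reader might also count Exhibit 7.2 as contradicting item 19. That item names symptoms and constipation and does not say GI treatment, so it is a matter of interpretation.

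The narrowing may be deliberate: constipation is the first target, and the non-constipation list includes enzymes, multivitamins and probiotics. If 70%–90% take enzymes (assumed), counting them leaves at most 120 to 40 of 400 on neither. Rewording items 20–21 with a reason would remove the inconsistency inside the SAP, but Protocol endpoint 19 would still have no output.

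Finally, no table shell for Exhibit 7.4 is visible, so it might display weekly values by group. Its description mentions neither absolute change nor medication class, and its model imposes a common time course.

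**Conclusion.** The point holds as a gap between listed items and described outputs, plus an unexplained change of model. Items 20 and 21 are answered only for constipation treatment. Item 22 is not described by class anywhere, and no exhibit is described as giving mean absolute PRO change among constipation-treated participants. Exhibit 7.4's coefficient is a valid visit-averaged difference and suits a mean-difference item; it cannot show differential change.

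The textual findings need no assumption. The sizes do: 40 to 288 misgrouped and a contrast of 0.8D to 0.1D rest on treatment shares that the documents do not give, and the additive coefficients rest on invented paths. A reader might infer that the reported difference would be badly diluted or would point the wrong way. The documents cannot establish that, since it depends on who takes what and how their scores differ. The endpoints are descriptive, the comparisons are confounded by indication either way, and the primary endpoint is unaffected. This should be corrected, but it does not threaten the study.

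**What to change.** 1. **Exhibit 7.4:** restore treatment × week and pancreatic status, with baseline as a modelled week, and report week-specific change by constipation treatment beside the visit-averaged difference.
2. **Item 22:** add an exhibit of mean absolute change (SD, 95% CI, n) at each follow-up, week 4 only for PAC-QOL, among participants receiving or initiating constipation treatment, overall and by Appendix D constipation class.
3. **Items 20–21:** add a three-group breakdown: any constipation treatment; non-constipation GI treatment only; neither. The first two combined against the third is the named contrast. Fix the class list before analysis and show results with and without pancreatic enzymes. PERT use also defines pancreatic insufficiency (SAP Exhibit 2.1), so when enzymes count as treatment, do not read the contrast adjusted for pancreatic status on its own.

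The cost is SAP wording and programming; the drugs are already ATC-coded for Exhibit 7.1. The model spends about 5 degrees of freedom (3 for the interaction with baseline modelled, 2 for three-level pancreatic status), or 3 for PAC-QOL. Class cells may be small: with half-width t × √(2w/n) and w = 0.12–0.52 assumed, a mean change has a half-width of 0.35–0.73 at n = 10 and 0.61–1.27 at n = 5. The group on neither may also be small once enzymes count. The breakdown does not match drug to symptom, so it does not by itself show whether a given symptom is adequately treated.

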Appendix B: Definitions of Constipation

Protocol-defined constipation: <3 bowel movements AND/OR BSS type 1 or 2.

Self-described constipation (based on disease-specific questionnaire)

- Definition 1: Answered “Constipated” for question 2 on disease-specific questionnaire
- Definition 2: Answered “Constipated” or “Alternating constipation and diarrhea” for question 2 on disease-specific questionnaire

Other alternative definitions to be considered:

- Proposed definition 1: <3 bowel movements (rationale: subset of the protocol definition)
- Proposed definition 2: BSS type 1 or 2 (rationale: subset of the protocol definition)
- Proposed definition 3: <7 bowel movements (rationale: the disease-specific questionnaire is a weekly survey, and having <7 bowel movements is equivalent to not having at least 1 bowel movement per day on average)

Appendix C: Pre-Specified GI Symptoms of Interest

PAC-SYM:

- Incomplete BMs (Q8)
- Straining or squeezing to try to pass a BM (Q11)
- Feeling you have to have a BM but cannot pass it (Q12)

PAGI-SYM:

- Regurgitation or reflux (fluid or liquid coming up) (Q18)
- Nausea (Q1)
- Vomiting (Q3)
- Upper abdominal pain (Q10)
- Loss of appetite (Q7)
- Stomach fullness (Q4)
- Bloating (Q8)
- Stomach for belly visibly larger (Q9)

Disease-specific questionnaire:

- Fecal incontinence

Appendix D: Medications of Interest

List of constipation medication/treatment of interest:

- Polyethylene glycol, Miralax, PEG, etc.
- Senna/Ex-Lax
- Lubiprostone
- Fiber supplements
- Linaclotide

List of non-constipation GI medication/treatment of interest:

- Acid suppressing agents: Proton Pump inhibitors; H2-Receptor antagonists; Others
- Antiemetics and antinauseants
- Anti-gas
- Anti-inflammatory agents
- Antispasmodic
- Appetite stimulants
- Bile acid derivatives
- Dopamine antagonists
- Drugs for non-acid reflux GERD
- Multivitamins and mineral supplements
- Pancreatic enzymes: relizorb, oral
- Probiotics

List of non-GI medication/treatment of interest:

- Erythromycin
- Azithromycin
- Drugs used in diabetes
